#### Efficacy outcome measures related to mosquito infection prevalence (oocyst prevalence):

11. Mosquito infection prevalence, assessed by DSF and measured as the proportion dissected with any number of oocysts, compared within groups between baseline and all feeding timepoints, and between groups at all feeding timepoints (timeframe: day 0 [baseline], 1, and 5)
12. Mosquito infection prevalence, assessed by DMFA and measured as the proportion dissected with any number of oocysts, compared within groups between baseline and all feeding

timepoints, and between groups at all feeding timepoints (timeframe: day 0 [baseline], 1, 5, and 14)

13. The association between naturally acquired anti-gametocyte immune responses and naturally acquired functional TRA on mosquito infection prevalence.

**Efficacy outcome measures related to mosquito infection intensity (oocyst density):**

14. Mosquito infection intensity, assessed by DSF and measured as the number of oocysts in dissected mosquitoes, compared within groups between baseline and all feeding timepoints, and between groups at all feeding timepoints (timeframe: day 0 [baseline], 1, and 5)

15. Mosquito infection intensity, assessed by DMFA and measured as the average number of oocysts in dissected mosquitoes, compared within groups between baseline and all feeding timepoints, and between groups at all feeding timepoints (timeframe: day 0 [baseline], 1, 5, and 14)

16. The association between naturally acquired anti-gametocyte immune responses and naturally acquired functional TRA on mosquito infection intensity.

**Efficacy outcome measures related to participant infectivity:**

17. Participant infection prevalence, assessed by DSF as the proportion of individuals infectious to any number of mosquitoes, compared within groups between baseline and all feeding timepoints, and between groups at all feeding timepoints (timeframe: day 0 [baseline], 1, and 5)

18. Participant infection prevalence, assessed by DMFA as the proportion of individuals infectious to any number of mosquitoes, compared within groups between baseline and all feeding timepoints, and between groups at all feeding timepoints (timeframe: day 0 [baseline], 1, 5, and 14)

19. The association between naturally acquired anti-gametocyte immune responses and naturally acquired functional TRA on participant infectivity.

**Efficacy outcome measures related to transmission reducing activity (reductions in oocyst intensity):**

20. Transmission-reducing activity in children and adults, measured as the percent reduction in mean oocyst intensity compared to experimental controls, compared within groups between baseline and all feeding timepoints, and between groups at all feeding timepoints (timeframe: day 0 [baseline], 5, 14, 28, 56, and 84)

21. Transmission-blocking activity in children and adults, measured as the percent reduction in mosquito infection prevalence compared to experimental controls, compared within groups between baseline and all feeding timepoints, and between groups at all feeding timepoints (timeframe: day 0 [baseline], 5, 14, 28, 56, and 84)

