#### Secondary efficacy objectives

- To assess the transmission-blocking activity of mAb TB31F assessed in the Direct Skin Feed (DSF) and DMFA at each dose level in naturally *P. falciparum* infected individuals
- To assess mosquito infection rate as measured by the proportion of dissected mosquitoes with any number of oocysts at each dose level in naturally *P. falciparum* infected individuals
- To assess the intensity of mosquito infection as measured by the average number of oocysts in dissected mosquitoes at each dose level in naturally *P. falciparum* infected individuals
- To assess participant infectivity after mAb TB31F administration at each dose level in naturally *P. falciparum* infected individuals

- To assess the transmission-reducing activity of participant serum after TB31F administration as assessed in the Standard Membrane Feeding Assay (SMFA) at each dose level in naturally *P. falciparum* infected adults and children

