**Outcome measures related to estimated inhibitory concentrations:**

25. The concentration of TB31F in serum that provides >80% reduction in the average proportion of infected mosquitoes as measured in DSF after TB31F administration
26. The concentration of TB31F in serum that provides >80% reduction in the average proportion of infected mosquitoes as measured in DMFA after TB31F administration
27. The concentration of TB31F in serum that provides >80% transmission blocking activity relative to experimental controls as measured in SMFA after TB31F administration
28. The concentration of TB31F in serum that provides >80% reduction in the average mosquito infection intensity (oocyst number) as measured in DSF after TB31F administration
29. The concentration of TB31F in serum that provides >80% reduction in the average mosquito infection intensity (oocyst number) as measured in DMFA after TB31F administration
30. The concentration of TB31F in serum that provides >80% transmission reducing activity relative to experimental controls as measured in SMFA after TB31F administration

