#### **Efficacy outcome measures related to transmission reducing activity (reductions in oocyst intensity):**

We will determine averaged within-individual percent reduction in the density of oocysts at days post-treatment (1, 5, 14) compared to baseline (day 0) for each group. This will be assessed through DMFA, DSF and SMFA and outcomes for these different feeding assays will be presented separately as percentage reduction (with 100% as total reduction of transmission, and negative values as enhanced transmission) with 95% confidence interval. For DMFA and DSF, these data will be analysed for all individuals who received the product per protocol without restrictions to baseline infectivity, and for those individuals who are infectious at baseline (i.e. infecting at least one mosquito with any number of oocysts). For SMFA, these data will be analysed for all individuals who received the product per protocol without restrictions to baseline infectivity in DMFA or DSF, as well as for the subset of individuals who are infectious at baseline. SMFA, an exploratory outcome, will be conducted after unblinding to allow testing of a realistic sub selection of test and control samples. Participants may have naturally acquired TRA due to exposure to gametocytes prior to enrollment; SMFA on baseline samples will allow us to identify these individuals. Additional samples that are most informative for determining the IC80 will be selected based on the ELISA data and tested in the SMFA. For this, one person not involved in data analysis will be unblinded and select samples based on ELISA values and treatment arm.

All analyses on within-individual percentage reduction in oocyst density will use a mixed effects negative binomial regression model with day of follow-up and dose of TB31F as fixed effects. A random intercept will be added to models to allow for participant-level variations (i.e. intra-cluster correlation).

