### Outcome measures related to estimated inhibitory concentrations:

Transmission blocking activity (TBA, the reduction in the proportion of infected mosquitoes) and transmission reducing activity (TRA, the reduction in oocyst numbers/infection intensity) will be determined for DMFA and DSF separately. Baseline infection prevalence and intensity estimates will be used to calculate relative reductions in these transmission measures during follow-up. For SMFA experiments, TRA will be quantified as the relative reduction in oocyst intensity for test samples (one feeder per test sample) compared to pooled naïve serum controls (two feeders). Samples may be tested in one or two independent SMFA experiments.

TRA values for each participant and time-point will be estimated using mixed effect negative binomial regression models with random intercepts for each experiment to account for between experiments differences in oocyst intensity that is achieved in control experiments (SMFA) or baseline measurements (DMFA/DSF).

TBA values for each participant and time-point will be estimated using mixed effect logistic regression models with random intercepts for each experiment to account for between experiments differences in oocyst prevalence that is achieved in control experiments (SMFA) or baseline measurements (DMFA/DSF). Of note: for SMFA TBA estimates are deemed to be less informative than TRA estimates due to the design of these experiments that aim for high oocyst prevalence and density in control experiments.

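### SMFA transmission-reducing activity is defined against experimental controls up to day 84, but its own analysis section measures it against the participant's day 0 at days 1, 5 and 14

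*SAP*

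**What the plan says.** **Definition.** In the SAP's Outcome Definitions, outcome 20 is TRA in children and adults, "measured as the percent reduction in mean oocyst intensity compared to experimental controls", with "timeframe: day 0 [baseline], 5, 14, 28, 56, and 84". It promises two kinds of comparison: within groups between baseline and later feeds, and between groups at each feed.

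**Which assay.** Outcome 20 does not name one. The Secondary efficacy objectives do: "To assess the transmission-reducing activity of participant serum after TB31F administration as assessed in the Standard Membrane Feeding Assay (SMFA"). Outcome 30 uses the same comparator and names the assay: "transmission reducing activity relative to experimental controls as measured in SMFA after TB31F administration".

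**Which control.** The analysis section on estimated inhibitory concentrations says that for SMFA "TRA will be quantified as the relative reduction in oocyst intensity for test samples" and that these are "compared to pooled naïve serum controls (two feeders"). Its model has a random intercept for each experiment.

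**Analysis.** The analysis section that carries outcome 20's heading specifies the "averaged within-individual percent reduction in the density of oocysts at days post-treatment (1, 5, 14) compared to baseline (day 0) for each group". It applies this to the direct membrane feeding assay (DMFA), direct skin feeding (DSF) and SMFA alike. Its negative binomial model has day and dose as fixed effects and a participant-level random intercept. The same section says that participants may already have naturally acquired TRA, and it calls SMFA exploratory.

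**The concern.** One outcome has two rules, which differ in comparator, days and model. A reduction against naïve serum counts all the activity in the sample, natural and antibody-derived. A reduction against the participant's own day 0 removes whatever was there before dosing. In a malaria-exposed population these can differ, so the TRA reported for each dose depends on which section the analyst follows.

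The days matter too. Outcome 20 runs to day 84, which is where duration of activity would show. The section written to analyse it stops at day 14. SMFA samples are to be chosen after unblinding, which is a further reason to settle the rule in advance.

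**Working it through.** The SAP gives no figure for this point, so there is nothing to reproduce. There are three checks.

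**1. Days.**

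| Source | Post-baseline days |
|---|---|
| Outcome 20, definition | 5, 14, 28, 56, 84 |
| TRA analysis section | 1, 5, 14 |

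Days 5 and 14 are common. Days 28, 56 and 84, three of the five defined, are absent from the analysis section. Day 1 is added, although it is not a day of this outcome. The analysis list matches the DMFA schedule in outcome 15 (days 1, 5, 14). DSF has only days 1 and 5 (outcome 14).

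**2. Comparator.** Let m_c, m_0 and m_t be mean oocyst intensity with naïve control serum, day-0 serum and day-t serum, on a common experimental scale.

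- Against control: TRA_0 = 1 − m_0/m_c and TRA_t = 1 − m_t/m_c.
- Against own day 0: R = 1 − m_t/m_0 = 1 − (1 − TRA_t)/(1 − TRA_0).

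For activity short of complete blocking, R equals TRA_t only when TRA_0 = 0. With TRA_t = 90%:

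| Assumed TRA_0 | R |
|---|---|
| 0% | 1 − 0.10/1.00 = 90% |
| 20% | 1 − 0.10/0.80 = 87.5% |
| 50% | 1 − 0.10/0.50 = 80% |
| 80% | 1 − 0.10/0.20 = 50% |

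Conversely, to reach R = 80% the TRA against control must be 1 − 0.20 × (1 − TRA_0), which is 80%, 84%, 90% or 96% for the same four baselines.

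The baselines are assumptions. The SAP uses 50% and 80% as cut-offs for classifying baseline TRA, not as expected values.

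**3. Model.** The model in the TRA analysis section has no term for the control feeders or for the experiment. As written it cannot return a reduction against control. The model in the inhibitory-concentration section includes the experiment intercept, because oocyst intensity in controls varies between experiments. The two sections therefore differ in estimand and in model.

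**The case against.** The strongest reply is that the inhibitory-concentration section settles the comparator. Its SMFA sentence is worded generally, and it estimates TRA by participant and by time-point with no day limit. The same part of the SAP allows the share of individuals above TRA thresholds and mean TRA by group and time-point, and it plans to model duration of activity. This stands in part. A reader might infer that activity to day 84 will not be analysed at all, and the SAP does not support that. But these group summaries and comparisons are optional, whereas outcome 20 promises them, and nothing there overrides the section written for outcome 20.

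A second reply is that outcome 20 itself contains a baseline comparison, so the analysis text may be a loose statement of it. Outcome 20, however, compares control-referenced values between days; it does not make day 0 the denominator. The day-0 contrast is not wrong in itself. A serum with 80% TRA at both times rightly shows zero change. It answers a different question, and one relevant to the exploratory objective on naturally acquired TRA.

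Third, the size is illustrative. A reader might take the 50% and 80% rows as what to expect in this population, but the SAP gives no frequency of natural TRA, and at 0% there is no difference.

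Fourth, a reader might extend the conflict to outcome 21, transmission-blocking activity. The section in question covers oocyst density only and sets no day-0 rule for blocking activity, so the contradiction is not shown there.

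**Conclusion.** The contradiction holds for outcome 20. That outcome does not name SMFA, but the secondary objective, outcome 30 and the inhibitory-concentration section together make the reading firm. Followed as written, the TRA analysis section produces a different quantity from the defined one whenever day-0 serum has activity.

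For a participant at 90% against control, the difference runs from nothing (baseline 0%) to 40 percentage points (baseline 80%), with the baselines assumed. The shift in a group estimate cannot be derived from the SAP. Days 28, 56 and 84 lack a committed within-group or between-group comparison for this outcome, but they are not absent from the plan.

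The primary efficacy outcome (DMFA at day 5) and the power calculation are unaffected. The weight of the point also depends on the standing of SMFA TRA, which the SAP lists as a secondary objective and elsewhere calls exploratory. It should be corrected before SMFA samples are selected.

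**What to change.** In the TRA analysis section:

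- Separate SMFA from DMFA and DSF.
- State that SMFA TRA is the reduction against the naïve-serum control of the same experiment, estimated with the experiment random intercept already given in the inhibitory-concentration section, for the samples tested at days 0, 5, 14, 28, 56 and 84. Referring to samples tested keeps this consistent with the planned sub-selection.
- Commit to outcome 20's within-group and between-group comparisons of those values.
- Label any SMFA reduction against own day 0 as a separate measure.
- Keep the day-0 reference for DMFA (days 1, 5 and 14) and DSF (days 1 and 5).
- Give SMFA TRA one status, secondary or exploratory, in both the objectives and the analysis section.

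The cost is SAP wording. Because the text refers to samples already planned for testing, it requires no extra assays.

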**Outcome measures related to the correlation between transmission assays:**

22. Correlation between transmission measures assessed by SMFA and DMFA in Malian adults and children

23. Correlation between transmission measures assessed by SMFA and Direct Skin Feed (DSF) in Malian adults and children

24. Correlation between transmission measures assessed by DMFA and DSF in Malian adults and children

**Outcome measures related to estimated inhibitory concentrations:**

25. The concentration of TB31F in serum that provides >80% reduction in the average proportion of infected mosquitoes as measured in DSF after TB31F administration
26. The concentration of TB31F in serum that provides >80% reduction in the average proportion of infected mosquitoes as measured in DMFA after TB31F administration
27. The concentration of TB31F in serum that provides >80% transmission blocking activity relative to experimental controls as measured in SMFA after TB31F administration
28. The concentration of TB31F in serum that provides >80% reduction in the average mosquito infection intensity (oocyst number) as measured in DSF after TB31F administration
29. The concentration of TB31F in serum that provides >80% reduction in the average mosquito infection intensity (oocyst number) as measured in DMFA after TB31F administration
30. The concentration of TB31F in serum that provides >80% transmission reducing activity relative to experimental controls as measured in SMFA after TB31F administration

## Analysis Methods

### Trial population

The primary safety and reactogenicity data will include all participants who meet the eligibility criteria, receive study product mAb TB31F, and for whom safety, efficacy and immunogenicity data are available.

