## Method

### Study design

The study is designed as a Phase 1/2a single-centre, double-blind, dose escalation, age de-escalation trial in malaria-exposed Malian adults and children. Two sequential stages of clinical research are conducted, each recruiting a distinct cohort of participants to confirm: 1. TB31F safety and 2. TB31F efficacy. Pharmacokinetic measurements will be performed in both safety and efficacy cohorts.

In total, a minimum of 165 participants will be recruited and enrolled; 45 adults and 30 children for the safety study, and ≥ 90 adults and children for the efficacy study. In the tables below, the cohorts are described with the number of participants, the duration of follow-up and the dose of TB31F administered.

*Table 1. Study design for Cohort 1 (Adults): Safety and pharmacokinetics (18-50 years of age)*

Group	Dose	N	Volume TB31F/Saline	Sample timepoints*	Safety follow-up after each dose administration
1	1A: Control (normal saline)	5	0.2 mL	Day 0 (Baseline), 1, 5, 7, 14, 21, 28, 42, 56, 84	Solicited local and systemic AEs (days 1-7); Unsolicited AEs (study duration); SAEs (study duration)
	1B: 10 mg mAb TB31F	10			
2	2A: Control (normal saline)	5	2 mL		
	2B: 100 mg mAb TB31F	10			
3	3A: Control (normal saline)	5	4 mL		
	3B: 200 mg mAb TB31F	10			

\* Group 1 participants will be followed-up until day 28

*Table 2. Study design for Cohort 1 (Children): Safety and pharmacokinetics in school age children (>10-15 years)*

Group	Dose	N	Volume TB31F/Saline	Sample timepoints	Safety follow-up after each dose administration
4	4A: Control (normal saline)	5	0.2 mL	Day 0 (Baseline), 1, 5, 7, 14, 21, 28, 42, 56, 84	Solicited local and systemic AEs (days 1-7); Unsolicited AEs (study duration); SAEs (study duration)
	4B: 10 mg mAb TB31F	10			
5	5A: Control (normal saline)	5	2.0 mL		
	5B: 100 mg mAb TB31F	10			

*Table 3. Study design for Cohort 2: Efficacy in a mixed age cohort (>10-50 years of age)*

Group	Dose	N	Volume TB31F/Saline	Sample timepoints	Safety follow-up after each dose administration
6.1	6AB: Control (normal saline)	15	0.6* mL	Day 0 (Baseline), 1, 5, 14, 21, 28, 56, 84	Solicited local and systemic AEs (days 1-7); Unsolicited AEs (study duration); SAEs (study duration)
	6B: 30 mg mAb TB31F	30	0.6* mL		
6.2	6AC: Control (normal saline)	15	2.0 mL		
	6C: 100 mg mAb TB31F	30	2.0 mL		

AE = Adverse events, SAE = Serious adverse events. Participants will be randomised in a 1:2:1:2 ratio to the 6AB, 6B, 6AC, or 6C group.

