#### Adherence and protocol deviations

Missing data will not be imputed due to the small number of participants in each group. Participants who miss an appointment date will be retained in the study and available data will be analysed. If human errors are made during TB31F administration, the actual administered dose and time will be used in analyses.

A best-worst case sensitivity analysis may be performed. Lack of precision is expected in some outcome measures, for instance estimates of (low) transmission reducing activity (TRA) by SMFA. For some analyses, we may thus use TRA estimates that are inferred from antibody concentration based on the best fit model for the association between antibody concentration and TRA. Details are provided on page 16.

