#### Safety outcome measures:

1. Occurrence of at least possibly related
  - a) solicited local and systemic adverse events (AEs) within 7 days of mAb TB31F administration
  - b) unsolicited AEs within 28 days of mAb TB31F administration
  - c) serious adverse events during the entire study period

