## Analyses in relation to endpoints

### Safety outcome analyses

- For each solicited (local or systemic) adverse event type, the number and proportion of participants experiencing that AE within the Protocol-defined timeframe will be tabulated by severity grade for each dose group and for the entire study population. This will also be tabulated for participants experiencing any solicited local, any solicited systemic and any unsolicited AE. Where applicable, we will compare these proportions between groups.

Relatedness (possibly, probably or definitely) of solicited AEs to TB31F administration may also be presented.

- For each related unsolicited adverse event type (categorized by MedDRA), the number of events per dose group and overall study population will be described and categorized by severity grade and relation to TB31F administration. (Outcome measure 1).
- The proportion of individuals with grade 1, 2 and 3 adverse events may be compared between groups.
- The total number of grade 1, 2 and 3 adverse events as count data may be compared between groups.
- Individual serious adverse events (SAEs) will be summarized, including relatedness to TB31F administration.
- Withdrawals due to AEs/SAEs will be summarized per group.

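### The SAP's only safety population, read as written, excludes all 55 planned saline controls and makes inclusion depend on efficacy and immunogenicity data

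*SAP*

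**What the plan says.** Under Analysis Methods, Trial population, the SAP states: "The primary safety and reactogenicity data will include all participants who meet the eligibility criteria". The sentence then adds that they must "receive study product mAb TB31F, and for whom safety, efficacy and immunogenicity data are available". No other sentence in the SAP defines a safety set. The wording under Efficacy outcome measures about participants who received the product per protocol applies to the feeding-assay analyses only.

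Other sections bear on it:

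- Study design, Tables 1 to 3, and Randomization: saline controls are randomised 1:2 against TB31F within each dose group, in both cohorts. The total is given as "In total, a minimum of 165 participants will be recruited and enrolled".
- Safety outcome analyses: solicited adverse events are "tabulated by severity grade for each dose group and for the entire study population". The SAP adds: "Where applicable, we will compare these proportions between groups".
- Adherence and protocol deviations: "Participants who miss an appointment date will be retained in the study and available data will be analysed".
- Safety outcome measures: the first window is defined as "solicited local and systemic adverse events (AEs) within 7 days of mAb TB31F administration".

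**The concern.** Safety is a primary objective in both cohorts, and the trial is placebo-controlled. The saline arms supply the background rate of adverse events against which events after TB31F are judged. A safety set that requires receipt of TB31F has no such comparator. TB31F dose groups could still be compared with one another, but none could be compared with saline.

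The second requirement, that efficacy and immunogenicity data be available, makes inclusion depend on what happens after dosing. A participant who is dosed, has an adverse event and leaves early may have incomplete data of these kinds. Excluding such participants could understate the adverse event rate. The requirement also cannot be applied reproducibly. The SAP does not say how much data counts as available. It lists no outcome for the immunogenicity of TB31F either; anti-drug antibody appears only in the abbreviations.

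**Working it through.** **Planned numbers, from Tables 1 to 3 under Study design**

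| Part | Saline | TB31F | Total |
|---|---|---|---|
| Cohort 1 adults (groups 1 to 3) | 3 × 5 = 15 | 3 × 10 = 30 | 45 |
| Cohort 1 children (groups 4 and 5) | 2 × 5 = 10 | 2 × 10 = 20 | 30 |
| Cohort 2 (groups 6.1 and 6.2) | 2 × 15 = 30 | 2 × 30 = 60 | 90 |
| All | 55 | 110 | 165 |

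The total of 165 reproduces the SAP's own figure. It is a minimum, because Cohort 2 is planned as at least 90.

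**Step 1: the condition of receiving TB31F.** All 55 saline participants fail it: 55/165 = 33.3%. At most 110/165 = 66.7% remain, with no control among them. By dose, the 110 are:

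- 10 mg: 10 (1B) + 10 (4B) = 20
- about 30 mg: 30 (6B)
- 100 mg: 10 (2B) + 10 (5B) + 30 (6C) = 50
- 200 mg: 10 (3B)

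**Step 2: comparison with the planned tabulations.** The safety tables are to cover each dose group and the entire study population. According to Randomization, a dose group contains its own control sub-group. Tables restricted to TB31F recipients would therefore show neither the whole dose group nor the whole study population.

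**Step 3: the data condition.** Adherence and protocol deviations keeps participants who miss a visit and uses whatever data they have. Trial population asks for three kinds of data to be available before a participant counts for safety at all. The two rules pull in opposite directions for anyone with incomplete follow-up.

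**Step 4: Cohort 1 (conditional).** Efficacy objectives appear only under Cohort 2. Of the measurements shared by the cohorts, Study design mentions only PK: "Pharmacokinetic measurements will be performed in both safety and efficacy cohorts". This implies that Cohort 1 has no feeding assays but does not say so. Outcomes 20 and 21 name no cohort, and serum is collected in Cohort 1. If there are none, the efficacy-data condition removes a further 50 TB31F recipients: 110 − 50 = 60, and 60/165 = 36.4%. Those left would be 30 at about 30 mg and 30 at 100 mg, with nobody at 10 mg or 200 mg. If SMFA were run on Cohort 1 serum, complete efficacy data would still not be assured, because the SAP plans SMFA on a selection of samples made after unblinding.

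**The case against.** The strongest reply is that the sentence is loose wording and not a real rule. The SAP often writes TB31F administration where blinded study product seems to be meant. The interim analysis section uses that term and IP administration for the same event. The outcome windows start from TB31F administration, although Tables 1 to 3 give the saline arms the same safety follow-up. On this view the intention to include controls is plain. It can be added that Safety outcome analyses never names saline, that its comparison is qualified by where applicable, and that the three kinds of data may be meant only where each applies. The protocol, which is not at hand, may also define the set properly.

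Part of this stands. A drafting slip is likely, the conflict with the safety tables has to be read through the Randomization section, and the Cohort 1 loss is only conditional. The concern about early withdrawal is also limited: Cohort 2 feeds are scheduled from days 0 and 1, and SAEs and withdrawals due to adverse events are summarised separately.

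It does not rescue the sentence. In the pharmacokinetic section, receiving mAb TB31F is meant literally, so the phrase has no settled looser meaning in this document. Correcting it would still leave the efficacy and immunogenicity condition in place. A better definition in the protocol would leave two rules in conflict, with the choice between them open after data are seen.

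**Conclusion.** The concern holds. As written, the SAP's only safety population excludes all 55 planned saline controls, 33% of the minimum 165, and leaves at most 110 participants with no placebo comparator. This follows from the wording and the planned arm sizes alone; it does not claim that the analysts intend it. The conflict with the safety tabulations and with the rule on missed visits lies within the SAP and does not depend on the protocol.

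Two further points are weaker. The reduction to at most 60 participants (36%) assumes that Cohort 1 has no efficacy assays. Bias from early withdrawals is possible, in the direction of understated adverse event rates, but its size cannot be derived from the SAP.

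The sentence must be corrected before analysis, because it governs a primary objective in both cohorts.

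**What to change.** Replace the sentence under Trial population with wording such as: The safety population comprises all participants who received any amount of study product (TB31F or saline), analysed by product and dose actually received, irrespective of the availability of efficacy or immunogenicity data. This restores all 165 planned participants (110 TB31F and 55 saline), provided all are dosed. It agrees with the existing rule that the dose actually administered is used in analyses.

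The new wording also drops the eligibility condition. That should be a deliberate choice: a participant dosed and later found ineligible was still exposed, and belongs in a safety set.

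In Safety outcome measures, start the adverse event windows from study product administration, so that they apply to the saline arms. Because the SAP refers its outcome definitions to protocol section 2, check that the two documents still agree after the edit. The efficacy sets can stay as they are.

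The cost is one sentence, one matching term and a consistency check against the protocol. No new data are needed and trial conduct does not change.
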